7.2.1. Withdrawal From the Use of Research Samples

Withdrawal From the Use of Samples in Future Research

The participant may withdraw consent for use of samples for research (refer to Long-term Retention of Samples for Additional Future Research in Appendix 3: Regulatory, Ethical, and Study Oversight Considerations). In such a case, samples will be destroyed after they are no longer needed for the clinical study. Details of the sample retention for research are presented in the main ICF.

7.3. Lost to Follow-up

A participant will be considered lost to follow-up if he or she repeatedly fails to return for scheduled visits and is unable to be contacted by the study site. A participant cannot be deemed lost to follow-up until all reasonable efforts made by the study-site personnel to contact the participant are deemed futile. The following actions must be taken if a participant fails to return to the study site for a required study visit:

- The study-site personnel must attempt to contact the participant to reschedule the missed visit as soon as possible, to counsel the participant on the importance of maintaining the assigned visit schedule, to ascertain whether the participant wishes to or should continue in the study.
- Before a participant is deemed lost to follow up, the investigator or designee must make every reasonable effort to regain contact with the participant (where possible, 3 telephone calls, emails, fax, and, if necessary, a certified letter to the participant's last known mailing address, or local equivalent methods). These contact attempts should be documented in the participant's medical records.
- Should the participant continue to be unreachable, they will be considered to have withdrawn from the study.

If a participant is lost to follow-up, every reasonable effort must be made by the study site personnel to contact the participant and determine the reason for discontinuation/withdrawal. The measures taken to follow up must be documented. Refer to Section 7.2, Participant Discontinuation/Withdrawal From the Study.

8. STUDY ASSESSMENTS AND PROCEDURES

Overview

The Schedule of Activities (SoA) summarizes the frequency and timing of metabolic, efficacy, safety, PROs, and other measurements applicable to this study. Additional visits may be required if, in the investigator's opinion, further clinical or laboratory evaluation is needed.

When an HIV-1 RNA repeat testing is required at an unscheduled visit to confirm protocol virologic rebound, an HIV-1 genotype/phenotype plasma sample and a plasma storage sample should also be drawn at the same unscheduled visit. Findings during these unscheduled visits or assessments need to be reported in the eCRF.

Some flexibility in the planning of the visits is allowed, however, the total treatment duration at the end of the study period should be 48 weeks. All study visits through Week 48 are to be completed within ± 7 days of the protocol-specified visit date.

All PRO assessments (BSQ-8D, HIV-SI and PGIC [including PGIC-S]) should be completed during the study visit before any tests, procedures, or other consultations to prevent influencing participant perceptions. The PGIC and PGIC-S should be completed after the participant completes the BSQ-8D and HIV-SI.

Other measurements may be done earlier than specified timepoints if needed. Actual dates and times of assessments (if applicable) will be recorded in the source documentation and CRF.

Additional serum or urine pregnancy tests may be performed, as determined necessary by the investigator or required by local regulation, to establish the absence of pregnancy at any time during the participation in the study. If a serum or urine pregnancy test is positive, the participant will be withdrawn from the study. For each participant, the maximum amount of blood drawn from each participant in this study will not exceed 261 mL.

Repeat or unscheduled samples may be taken for safety reasons or for technical issues with the samples or for confirmation of virologic rebound.

Sample Collection and Handling

The actual dates and times of sample collection must be recorded in the CRF or laboratory requisition form.

Refer to the Schedule of Activities (SoA) for the timing and frequency of all sample collections.

Instructions for the collection, handling, storage, and shipment of samples are found in the laboratory manual that will be provided. Collection, handling, storage, and shipment of samples must be under the specified, and where applicable, controlled temperature conditions as indicated in the laboratory manual

Study-Specific Materials

The investigator will be provided with the following supplies:

- Investigator's Brochure for D/C/F/TAF¹⁹
- pharmacy manual/study site investigational product and procedures manual
- laboratory manual and laboratory supplies
- Electronic Data Capture (eDC) Manual
- sample ICF
- Interactive Web Response System manual
- Dual-energy X-ray absorptiometry (DEXA) manual
- Patient Reported Outcomes (PROs) manual
- Contact Information Page

8.1. Assessments

8.1.1. Primary Endpoint (Percent Change in Body Weight)

Body weight will be evaluated at time points specified in the Schedule of Activities (SoA). Body weight will be measured using a calibrated scale. Attention should be given to weigh the participant on the same scale through the duration of the study. Participants should be weighed wearing underwear and a gown. Participants will be instructed to take off their shoes and to empty their bladders before being weighed. If disrobing for weighing is logistically impossible, the participant must be dressed as lightly as possible, with consistency from visit to visit. The scale should be calibrated according to the manufacturers specifications and at the frequency recommended by the manufacturer before the first participant is weighted. Calibration must be documented in the calibration log.

8.1.2. Metabolic Assessments

[figure not shown]
Systolic and diastolic blood pressure (SBP, DBP), pulse rate (supine after at least 5 minutes rest) will be recorded in a quiet setting without distractions, at the time points specified in the Schedule of Activities (SoA). Blood pressure and pulse/heart rate measurements will be assessed with a completely automated technique. Manual techniques will be used only if an automated device is not available. Body Mass Index will be calculated using body weight collected as described in Section 8.1.1 and height measured at screening. Height will be measured using a wall-mounted stadiometer or one mounted on a balance beam scale, whichever is most appropriate for the individual participant. Participants should be wearing socks or barefoot and should not be wearing shoes.

Body composition will be assessed at time points specified in the Schedule of Activities (SoA) via whole body DEXA scans. DEXA scans may be performed between screening and baseline (+2 weeks), at Weeks 24, 48, and the ESID visit (±10 days) (only to be performed at ESID if the last scan is more than 12 weeks from the date of the ESID visit and the ESID visit takes place before Week 48). A rescan for technical reasons at all scheduled time points is allowed within 2 weeks. A complete

description of the procedures for the DEXA scans will be provided in the DEXA manual. Reading of the DEXA scans will be performed centrally.

Waist circumference will be measured at time points specified in the Schedule of Activities (SoA). Waist circumference will be measured with the participant standing, wearing underwear, with or without a gown. The measurement will be performed at a level midway between the superior aspect of the iliac crests and the lower lateral margin of the ribs (see Figure 2). The measurement need not be at the level of the umbilicus. The measuring tape will be kept horizontal. Non-alcoholic fatty liver disease (NAFLD) Fibrosis and hypertension, age, insulin, resistance (HAIR) scores will be calculated based on receipt of central laboratory assessments and clinical status of the participant (Appendix 2: Clinical Laboratory Tests and Calculations)

Figure 2: Waist Circumference Measurement

Patient Standing, tape horizontal at level between Left Lateral Rib Margin and Superior Iliac Crest

Fasting clinical laboratory tests will be assessed at time points specified in the Schedule of Activities (SoA) to assess changes in the following metabolic parameters:

• lipids, calculated homeostatic model assessment of insulin resistance (HOMA-IR), HbA1C, leptin, adiponectin, and alpha melanocyte-stimulating hormone. If a participant has not fasted prior to the visit, the visit may proceed, but participant must return within 72 hours in a fasted state to have a blood draw for the metabolic assessments.

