Body weight	X	X	Х	Х	Х	Х	Х	Х	X	X	Attention should be given to weigh the participant on the same scale through the duration of the study. Participants should be weighed wearing underwear and a gown; participants will be instructed to take off their shoes and to empty their bladders before being weighed. Note: if disrobing for weighing is logistically impossible, the participant must be dressed as lightly as possible, with consistency from visit to visit
Waist Circumference Measurement	X	X	Х	X	X	X	Х	Х	Х		Measured with the participant standing, wearing underwear, with or without a gown. The measurement will be performed at a level midway between the superior aspect of the iliac crests and the lower lateral margin of the ribs. The measurement need not be at the level of the umbilicus. The measuring tape will be kept horizontal.
Body Composition via DEXA scan		X			X			Х	Х		Performed between screening and baseline (+2 weeks), at Weeks 24, 48, and the ESID visit (±10 days) (only to be performed at ESID if the last scan is more than 12 weeks from the date of the ESID visit and the ESID visit takes place before Week 48). A rescan for technical reasons at all scheduled time points is allowed within 2 weeks.
Complete physical examination	X	X						X	X		
Symptom-directed physical examination			X	X	X	X	X			X	May be conducted at all other scheduled/unscheduled study visits based on reported safety or tolerability issues.
Concomitant medications	X	X	X	X	X	X	X	X	X	X	

Phase	Screeninga	Baseline		48-W	eeks Tre	atment P	hase ^c	ESIDe	30-Day FU ^f	Remarks	
Visit		Day 1 ^b	Week 4	Week 12	Week 24	Week 28 ^d	Week 36	Week 48			
Study Procedures											
Adverse events (AEs)	X	X	X	X	X	X	X	X	X	X	In the setting of a suspected renal AE, serum creatinine and urine chemistry will be assessed (creatinine, sodium, phosphate, glucose, protein, albumin).
Fasting Clinical Laboratory Tests											
Chemistry profile	X	X	X	X	X	X	X	X	X	X	
Metabolic profile		X			X			X	X		If a participant has not fasted prior to the visit, the visit may proceed, but participant must return within 72 hours in a fasted state to have a blood draw.
Leptin and Adiponectin		X			X			X	X		
Alpha Melanocyte-Stimulating Hormone		X			X			X	X		
Hematology profile	X	X	X	X	X	X	X	X	X	X	
eGFRcr	X	X	X	X	X	X	X	X	X	X	eGFRcr by Cockcroft Gault
Urinalysis	X	X	X	X	X	X	X	X	X	X	Dipstick. If dipstick results are abnormal, the sediment will be examined microscopically.

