6. STUDY INTERVENTION

6.1. Study Interventions Administered

At the baseline visit (Day 1), eligible participants will be randomized in a 1:1 ratio to the Immediate Switch Arm (switch to D/C/F/TAF FDC) or the Delayed Switch Arm (maintain current INI + TAF/FTC ARV regimen). Randomization will be stratified by sex (Male or Female) and race (Black/African American or Non-Black/African American) at Baseline.

- Immediate Switch Arm: D/C/F/TAF FDC (DRV 800 mg + COBI 150 mg + FTC 200 mg + TAF 10 mg) once daily for 48 weeks.
- Delayed Switch Arm: continue current INI + TAF/FTC ARV regimen for 24 weeks. After 24 weeks participants will switch to a regimen of D/C/F/TAF FDC (DRV 800 mg + COBI 150 mg + FTC 200 mg + TAF 10 mg) once daily for an additional 24 weeks.

Participants randomized to the Immediate Switch Arm must start D/C/F/TAF FDC within 24 hours of the Baseline visit. D/C/F/TAF FDC tablet must be taken orally with food. Participants will be counseled to swallow D/C/F/TAF FDC tablet whole once daily at approximately the same time each day, according to their preference. D/C/F/TAF is to be taken with approximately 240 mL (8 ounces) of water. The D/C/F/TAF FDC tablet should be swallowed whole; alternatively, for participants who are unable to swallow the tablet whole, D/C/F/TAF FDC may be split into 2 pieces using a tablet-cutter, and the entire dose should be consumed immediately after splitting. Participants should not attempt to dissolve the tablet in water.

D/C/F/TAF FDC administration must be captured in the source documents and the CRF. Study-site personnel will instruct participants on how to store D/C/F/TAF FDC for at-home use as indicated for this protocol.

If participants notice that they have missed a D/C/F/TAF FDC intake and it is still within 12 hours of their regular dosing time, they should take the D/C/F/TAF FDC immediately with food. Participants can then continue their usual dosing schedule. If participants notice that they have missed a dose more than 12 hours after the time it is usually taken, they should be instructed not to take it and simply resume the usual dosing schedule. Participants should not take a double dose to make up for a missed dose.

Instructions regarding how to take D/C/F/TAF FDC tablet, what to do if a dose is missed and how to store the D/C/F/TAF FDC tablet will be provided on the wallet (study) card.

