2.2. Visit Windows

As subjects do not always adhere to the protocol visit schedule, the following rules are applied to assign actual visits to analysis visits. Listed below are the visit windows and the target days for each visit. The reference day is Study Day 1. If a subject has 2 or more actual visits in one visit window, the visit closest to the target day will be used as the protocol visit for that visit window. The other additional visit(s) will not be used in the summaries or analyses, but they can be used for determination of clinically important endpoints. If 2 actual visits are equidistant from the target day within a visit window, the later visit is used.

All assignments will be made in chronological order. Once a visit date is assigned to a visit window, it will no longer be used for a later time point except for the endpoint. Listed below (Table 2) are the analysis time points (week), visit windows and the target days for each visit defined in the protocol during the treatment phase. The time intervals will be used for reporting of metabolic/weight, efficacy, and safety data.

Table 2. Visit Windows

	Immediate Switch Arm - Time	Delayed Switch Arm - Time	
Analysis	Interval	Interval	Target Time
Time Point a	(Day)	(Day)	Point (Day)
Screening	Day-42 - <day 0<="" td="">Day-42 - <day 0<="" td="">-∞	</day>	</day>	Day-42 - <day 0<="" td="">-∞	</day>	-∞
Baseline b	≤Day 1	≤Day 1	1
Week 4	Day 2 – Day 56	Day 2 – Day 56	29
Week 12	Day 57 – Day 126	Day 57 – Day 126	85
Week 24	Day 127 – Day 210	Day 127 – Day 182	169
Week 28	NA	Day 183 – Day 224	197
Week 36	Day 211 – Day 294	Day 225 – Day 294	253
Week 48	Day 295 – Day 378	Day 295 – Day 378	337

^a For subjects discontinuing treatment early, data collected at that visit will count towards the time interval based on days relative to baseline.

Note: Target Time Point (Day)=Week $x\times7 +1$; Time Interval (Day), for example, Start day=127=(85+169)/2 and then obtain the previous interval End day=127-1=126. Similarly, for other intervals' Start day and End day.

Phases will be constructed for each subject as follows for adverse events, concomitant therapies, and for the determination of the worst-case/toxicity/change in the cross-tabulations.

^b The baseline visit (Day 1) cannot proceed until the investigator has received all results of the screening visit and participant eligibility has been confirmed.

Trial phase	Start date	End date

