2.6. Study Day and Relative Day

Study Day 1 or Day 1 refers to the start of the first study agent administration or randomization date. If subjects start medication a day after baseline/screening visit, actual treatment administration date will be used as Day 1 instead of screening/baseline visit date.

All metabolic, efficacy and safety assessments at all visits will be assigned a day relative to this date.

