2.7. Baseline and Endpoint

Baseline is defined as the last observation prior to the start of the first study agent administration or randomization date.

Endpoint is defined as the last available postbaseline result within the analysis period. Unscheduled visit results are included in this definition and will be considered as the endpoint value if the unscheduled visit result is the last postbaseline result available within the analysis period.

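### A baseline DEXA done within the protocol's window but after Day 1 cannot serve as baseline under the SAP, so that participant has no change from baseline in body composition

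*Protocol*

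**What the plan says.** **Protocol.** Section 8.1.2 states that "DEXA scans may be performed between screening and baseline (+2 weeks"), and the Schedule of Activities (1.3) has the same one-sided allowance: "Performed between screening and baseline (+2 weeks), at Weeks 24, 48, and the ESID visit (±10 days"). It schedules one baseline DEXA, then Weeks 24 and 48, with an early-discontinuation scan under conditions. There is no Week 4 DEXA. Section 8.1.2 adds: "A rescan for technical reasons at all scheduled time points is allowed within 2 weeks". Section 6.1 fixes when the new regimen starts: "Participants randomized to the Immediate Switch Arm must start D/C/F/TAF FDC within 24 hours of the Baseline visit".

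**SAP.** Section 2.7: "Baseline is defined as the last observation prior to the start of the first study agent administration or randomization date". Section 2.6: "Study Day 1 or Day 1 refers to the start of the first study agent administration or randomization date". Table 2 in Section 2.2 sets Baseline at Day 1 or earlier and Week 4 at Days 2 to 56 in both arms, and Section 2.2 says of these windows: "The time intervals will be used for reporting of metabolic/weight, efficacy, and safety data".

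**Endpoints.** SAP 6.2.1 lists change from Baseline in DEXA body composition at Week 24 (both arms) and at Week 48 (Immediate Switch only). SAP 6.2.1.1 adds a consistency comparison of body composition and of percent change in visceral adipose tissue: Baseline to Week 24 in the Immediate Switch Arm against Week 24 to Week 48 in the Delayed Switch Arm.

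**The concern.** The two documents use different boundaries for the same scan. The protocol lets the first DEXA follow Day 1; the SAP does not let an observation after Day 1 be a baseline. Because only one baseline scan is scheduled, there is normally nothing to replace it. Applied as written, the SAP turns a compliant scan into an unplanned Week 4 value and leaves the participant with no reference for the body-composition endpoints.

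What is at stake is avoidable loss of data. There is also a risk that whoever programs the analysis has to choose between dropping compliant scans and applying an unwritten rule, in an open-label trial, with the data already visible.

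**Working it through.** **1. Reproduce the SAP windows.** The SAP illustrates its midpoint rule with "Start day=127=(85+169)/2 and then obtain the previous interval End day=127-1=126". Applied to the target days 29, 85, 169, 197, 253 and 337:

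- Week 12 starts at (29 + 85)/2 = 57, so Week 4 ends on Day 56.
- Week 24 starts at (85 + 169)/2 = 127.
- Immediate Switch: (169 + 253)/2 = 211 and (253 + 337)/2 = 295.
- Delayed Switch: (169 + 197)/2 = 183, (197 + 253)/2 = 225, then 295.

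All agree with Table 2. The Day 2 start of Week 4 is not a midpoint, since (1 + 29)/2 = 15. It follows from the explicit rule that Baseline ends on Day 1.

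**2. Place each permitted baseline scan.**

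| Scan date | Study day | SAP window, both arms |
|---|---|---|
| Baseline visit | 1 | Baseline |
| Visit +1 to +14 days | 2 to 15 | Week 4 |
| Rescan 14 days after a +14-day scan | 29 | Week 4 |

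If the first dose is taken the day after the visit, SAP 2.6 moves Day 1 by one day. Visit +1 becomes Day 1, and visit +2 to +14 (Days 2 to 14) still fall in Week 4.

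**3. Apply the baseline definition.** A scan on Day 2 or later is not before first administration or randomization, so it fails SAP 2.7 whatever the window label.

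**4. Look for an exception.** The only other reference rule in the SAP, the timepoint closest to first drug intake, is in Section 7.3.2 and concerns vital signs, weight and BMI. It does not mention DEXA.

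**5. Size, by scenario.** The documents do not give the share p of participants whose only first scan is late. Assume p is equal in the two arms, the SD is unchanged, and everyone else has a usable pair of scans. Then n = 110(1 − p), and the standard error is multiplied by 1/√(1 − p):

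| p (assumed) | n of 110 | SE factor | Rise |
|---|---|---|---|
| 10% | 99 | 1.054 | 5% |
| 20% | 88 | 1.118 | 12% |
| 30% | 77 | 1.195 | 20% |

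**6. Cost of accepting late scans.** The Week 24 target is Day 169, which is 168 days after Day 1. For an Immediate Switch participant, if change were linear in time (an assumption), a Day 15 baseline would miss 14/168 = 8% of the 24-week change. A rescan as late as Day 29 would miss 28/168 = 17%. A Delayed Switch participant is still on the pre-study regimen at that time.

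**The case against.** **Whether any scan is affected.** The scanning window opens at screening, which lasts about 30 days and up to 6 weeks, so sites have ample time to scan before Day 1. Nothing in the documents shows that any baseline scan was late. This stands: the affected group may be small or empty.

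**Whether a late scan really becomes Week 4.** SAP 2.2 assigns visits to windows, and the scan is scheduled under the Baseline visit, so it might keep that label. SAP 2.6, however, gives every metabolic assessment a day relative to Day 1. In any case, the body-composition endpoints are listed only at Weeks 24 and 48, so the label matters little. The loss comes from SAP 2.7.

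**Wording and missing documents.** The +2 weeks allowance is loosely phrased, but it appears the same way in both protocol places beside a two-sided ±10 days, so after-baseline is the natural reading. The DEXA manual and the data presentation specifications are not available and could contain a rule. Even so, SAP 2.7 defines baseline without exception and is where the rule belongs.

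**Stronger readings that a reader might infer.**

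- *A leading secondary objective is damaged.* Body composition is one of several unranked secondary metabolic objectives. SAP 6.2.2.1 analyses these descriptively. Protocol 9.4.3.1 names the mixed model for change endpoints, but neither document gives DEXA power or alpha.
- *Visceral fat is lost at Week 48 as well.* The SAP names visceral fat only in the consistency comparison. Its Delayed Switch side runs from Week 24 to Week 48 and uses no baseline scan.
- *The loss is unequal by arm and biases the comparison.* This is possible with open-label scheduling, but nothing in the documents shows it.

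**Conclusion.** The mismatch is real on the text. A participant whose sole first DEXA is compliant but after Day 1 has no change from baseline in body composition: at Week 24 in either arm, and also at Week 48 in the Immediate Switch Arm. An Immediate Switch participant also drops out of the Baseline-to-Week-24 side of the visceral-fat and body-composition consistency comparisons. This holds whether the endpoint is modelled or summarised, because the change cannot be calculated.

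The size is unknown. The 5, 12 and 20% rises in standard error are illustrations under assumed late-scan rates, not estimates. The conclusion assumes that +2 weeks means after the baseline visit and that no unseen document overrides SAP 2.7. The primary weight endpoint does not use DEXA and is unaffected. The point deserves correction because stated rules discard compliant data and the repair is cheap; it does not threaten the trial's main result.

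**What to change.** Add to SAP 2.7 a rule along these lines: *For DEXA, baseline is the last evaluable scan before first study agent administration or randomization; if there is none, it is the first evaluable scan within the protocol baseline window, including a permitted technical rescan.*

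The order matters. A rule that simply took the scan closest to Day 1 could replace a valid scan on Day −5 with an on-treatment rescan on Day 3.

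In SAP 2.2, exempt scans used as baseline under this rule from the Week 4 window. Flag them, report their number by arm, and repeat the body-composition and visceral-fat summaries without them.

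The cost is one rule, one window exception, one flag and one sensitivity analysis. The downside is that some Immediate Switch baselines would follow a short period on the new regimen, which slightly dilutes the measured change; the sensitivity analysis shows whether that matters.
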